#### Inferential Analyses

In univariate analysis, paired T-test or Wilcoxon Signed Rank Test will be applied to identify the difference in scores for primary and secondary outcomes of interest for Time-0 and Time-1 in this study. An intergroup mean difference will be calculated based on the formula

mentioned below to confirm the difference between the intervention and the control group's primary and secondary outcomes variables shown in Table 3.15.

Intergroup mean difference = [(mean preI – mean postI) – (mean preC – mean postC)], where preI = pre-intervention in intervention group;

post = post-intervention in intervention group;

prec = pre-intervention in comparison group and

postC = post-intervention in comparison group.

In multivariable analyses, three types of inferential analyses will be considered. They are repeated measures ANOVA, ANCOVA, generalised linear mixed model (GLMM) (Mixed Model Repeated Measure (MMRM) or logistic GLMM). A mixed model general linear model design like repeated measures ANOVA and ANCOVA helped address differences between two independent measures while also exposing subjects to repeated measures (Green & Salkind, 2011; Leppink, 2018). However, they only allowed listwise deletion and last observation carried forward (LOCF) for dropout cases. This may lead to reduced power and biases in the estimation. Therefore, given the missingness for dropout 20%) and small sample size, MMRM or logistic GLMM is superior in conserving the power of the current dataset. MMRM or logistic GLMM is also a likelihood-based statistical approach for handling repeated non-independent measures data collection overtime points. This model uses an unstructured time and covariance structure that (1) avoids model misspecification and (2) its unbiasedness for data that are missing completely at random (MCAR) or missing at random (MAR)(Bell & Rabe, 2020; Mallinckrod+ et al., 2008). GLMM was chosen for analysis instead of GEE, as the formal is an extension of MMRM, providing a more consistent estimate of the fixed effects and given MAR for missingness in the current dataset (Liu and Zhan, 2011; Davis, 2014).

All primary and secondary outcomes variables will be treated as continuous variables and analysed using MMRM. Whereas EQ-5D (residuals were non-normal distributed when modelled with MMRM) will be dichotomised based on median (0= 'no problem' index  $\geq$ 0.928 1= "problematic" index < 0.928) and analysed with logistic GLMM. Interaction terms were created and tested for the first-order main effect. Final models were assessed for assumptions compliance regarding the normal distribution of the residuals, homoscedasticity and random effect coefficient(Schielzeth et al., 2020). Model fitness was evaluated using the likelihood-ratio test, AIC, BIC and coefficient of determination  $r^2$ .

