## Null hypothesis (H0):

There is no significant difference in the mean differences for the **primary outcomes variables and secondary outcomes variables** among B40 respondents at the community housing project in the intervention compared to the control. **Alternative hypothesis:** There is significant difference between the mean differences of the **primary outcomes variables and secondary outcomes variables** among B40 respondents at the community housing project in the intervention in comparison to the control arm.

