#### 3.2.3.1a Outcome Evaluation

Outcome evaluation is to evaluate whether the psychosocial intervention worked on those who received the ReSHape intervention module. An online Quasi-experimental study will be conducted to evaluate the effectiveness. Standardized tools were utilised to record baseline data are as below:

**Primary Outcomes :** Patient Health Questionnaire (PHQ-9), Generalized Anxiety disorders (GAD-7), health-related quality of life (EQ-5L-5D)

**Secondary Outcomes:** Self-reported weight and height, Psychosocial indicators Resilience Scale 14-items (RS-14) and Health Literacy 12-items, Santa Clara Strength of Religious Faith is a 5items, Poverty Attribution 21-items, Mental Help-Seeking Attitudes Scale (MHSAS) and Self-Stigma of Seeking Help (SSOSH) scale

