#### 3.2.5 Sample size calculation

Based on Mathias et al. (2018) study on the effectiveness of resilience intervention to improve the mental status among young women in India and a local study for the effectiveness of mindfulness among university students, the effect size of the pre-test and post-test intervention were (d=0.42)(Phang, Chiang, et al., 2015). The sample size was calculated using G\*Power version 3.1.9.4, and the estimated sample size was 50 cases in each arm (after inflated with a 20 % reserved rate). The initial required sample size for the entire study was calculated based on a 0.05 precision level and a 95 per cent confidence interval with the power of 80 per cent. Experts in module development have suggested that the validation of the modules is similar to the validation for research instruments (Sidek, 2005). Therefore the sample size for validation of modules was 30 respondents, and a similar sample size was observed in other modules' development studies (Ahmad et al.; Talib et al., 2015)

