#### 3.2.6.5 European Health-Related Quality of Life, EQ-5D-5L

EQ-5D-5L is a standardised measure of Health-Related Quality of Life (HRQoL) developed by the Euro-Qol Group to provide a simple, generic questionnaire for clinical

and economic appraisal or population health status surveys. The EQ-5D-5L is part of the EQ-5D family of instruments.

EQ-5D-5L comprised the descriptive system (EQ-5D) and a visual analogue scale (EQ-VAS) that required a few minutes to complete.

The descriptive system is divided into five dimensions, providing information on the respondent's perceptions of their health status, including mobility, self-care, usual activities, pain or discomfort, and anxiety or depression. Each dimension is rated based on five response levels which include 1 = no problems, 2 = slight problems, 3 = moderateproblems, 4 = severe problems or 5 = unable to/extreme problems(Oemar & Janssen,2013).

For instance, if a respondent scored 12345 for the mobility domain, the interpretation is no problems with mobility, slight problems with self-care (washing or dressing), moderate problems with doing usual activities, severe pain or discomfort and extreme anxiety or depression. Each health state can potentially be assigned a summary index score based on societal preference weights for the health state. This health state index scores generally range from less than 0 (where 0 is the value of a health state equivalent to dead; negative values representing values as worse than dead) to 1 (the value of full health), with higher scores indicating higher health utility(Oemar & Janssen, 2013). Each country has its own standardised value set, generated through a local study. The value set for Malaysia was published by Shafie, Vasan Thakumar, Lim, Luo, et al. (2018).

Visual analogue scale (EQ-VAS) records the respondent's overall current health on a vertical visual analogue scale, where the endpoints are labelled 'The best health you can imagine and 'The worst health you can imagine. The EQ-VAS provides a quantitative measure of the patient's perception of their overall health. The respondents need to mark on a scale ranging from 0 to 100.

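### The EQ-5D primary outcome is cut at 0.928 and tested on an odds scale, so its only stated between-arm test does not address the mean-difference hypothesis

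*Protocol*

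**What the plan says.** Section 3.2.3.1a (Outcome Evaluation) lists three primary outcomes: PHQ-9, GAD-7 and "health-related quality of life (EQ-5L-5D"). The first Phase 2 null hypothesis in section 1.6.2 covers primary and secondary outcomes alike: "There is no significant difference in the mean differences for the" outcome variables between intervention and control.

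Section 3.2.7.2 (Inferential Analyses) has three relevant statements:

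- For the primary and secondary outcomes, "An intergroup mean difference will be calculated based on the formula" given there, which is the mean change in the intervention arm minus the mean change in the control arm. The tests named beside it are paired comparisons of T0 with T1.
- As the general rule, "All primary and secondary outcomes variables will be treated as continuous variables and analysed using MMRM".
- As the exception, "EQ-5D (residuals were non-normal distributed when modelled with MMRM) will be dichotomised based on median". The upper category (0.928 and above) is labelled as having no problem. The lower one is labelled problematic, "index < 0.928) and analysed with logistic GLMM".

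Section 3.2.6.5 describes the index as running from below 0 "to 1 (the value of full health), with higher scores indicating higher health utility". Table 3.7 in section 3.2.7.1 lists EQ-5D as both continuous and categorical.

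**The concern.** A logistic model on a dichotomised index answers a different question from the stated hypothesis. It asks whether the odds of being below 0.928 differ between arms, not whether mean utility changed by a different amount. If that model is the only between-arm test of EQ-5D, the hypothesis for this primary outcome goes untested.

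Two further matters are at stake. The reason given for the split is a property of fitted residuals, so the scale, model and threshold of a primary outcome may have been chosen after outcome data were seen. The split also treats a move from 0.60 to 0.90 as no change and a move from 0.92 to 0.93 as a full response. That discards information in a small study whose stated reason for choosing mixed models is to conserve power.

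**Working it through.** **Step 1: hypothesis against analysis.**

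- Hypothesis (1.6.2): difference between arms in mean change.
- Calculated quantity (3.2.7.2): (mean pre − mean post) in the intervention arm minus the same in the control arm. This matches the hypothesis, but no between-arm test or interval is attached. The paired tests are within-arm.
- Model-based test (3.2.7.2): logistic GLMM on index below 0.928, giving an odds ratio. This does not match.

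**Step 2: when the choice was made.** The residuals are reported as already examined under MMRM. MMRM needs repeated measurements, and the Phase 1 survey is cross-sectional. The same section also refers to missingness in the dataset in hand. Both point to T0/T1 data having been modelled. The sample and time point behind the 0.928 median are not stated.

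**Step 3: inputs for the size.** Two-sided 0.05 (sidedness is not stated, so this is assumed) and 50 per arm including a 20% reserve (section 3.2.5), so about 50 × 0.8 = 40 evaluable. For effect size, section 3.2.5 says "the effect size of the pre-test and post-test intervention were (d=0.42"), taken from other studies and not specific to EQ-5D. The protocol gives no EQ-5D mean, SD, ceiling share or power.

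The plan's 50 per arm does not reproduce from these inputs. A two-sample two-sided comparison needs 2(1.96 + 0.842)²/0.42² = 89 per arm, or 112 after dividing by 0.8. A paired two-sided test needs 47, or 59. That is a separate matter and nothing below depends on it.

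**Step 4: loss if the index were normal.** The efficiency of a median split relative to a comparison of means, for a pure shift, is 4 f(m)² σ², where f(m) is the density at the median. For a normal outcome this is 4 × 1/(2πσ²) × σ² = 2/π = 0.637, a loss of 36%.

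- Continuous power is Φ(0.42√(n/2) − 1.96): Φ(0.14) = 55.6% at 50 per arm, and 46.7% at 40.
- Split: the proportions are Φ(−0.21) = 0.417 and Φ(0.21) = 0.583. Power from the two-proportion formula is 38.2% at 50 and 31.6% at 40.
- For 80% power: 89 per arm continuous, 141 split.

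These are single comparisons of two arms, with no baseline or within-person correlation. They illustrate the loss and are not the power of the planned model.

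**Step 5: loss if the index is not normal, as the protocol says of its residuals.** The same formula gives:

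- beta(8,2) 0.61; beta(6,1) 0.69; beta(9,1) 0.77
- gamma(2) 0.79; lognormal with sigma 0.5, 0.93; exponential 1.00

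A simulation (6,000 trials per setting, 50 per arm) used a latent normal index with control median 0.928, capped at 1, and a shift of 0.42 latent SD. Power for the t-test against the split was:

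- 20% at the ceiling: 50.1% against 38.6%, efficiency 0.72
- 30%: 46.8% against 39.6%, efficiency 0.81
- 40%: 42.8% against 38.2%, efficiency 0.87
- 49%: 40.4% against 39.4%, efficiency 0.97

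The last setting implies a latent SD of 2.87 and is only a limiting case. Over these skewed and ceiling shapes the loss runs from about 0% to 39% (1 − 0.61). Symmetric shapes fall outside that range in both directions (uniform 0.33, Laplace 2.0), so the shape decides the answer. All these figures take 0.928 to be the trial sample's own median.

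**Step 6: label.** Section 3.2.6.5 sets full health at 1. An index from 0.928 to below 1 is therefore not full health, yet it falls in the category labelled as having no problem.

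**The case against.** The exception is declared openly. The EQ-5D sentence is set against the general rule, Table 3.7 lists EQ-5D as continuous and categorical, and logistic GLMM is named among the candidate models. A reader might infer that the protocol contradicts itself by calling all primary outcomes continuous and then splitting one. It does not, because this is a stated rule with a stated exception. The mismatch that stands is with the hypothesis.

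Nor is the mean difference abandoned, since section 3.2.7.2 still calculates it for the primary outcomes. What is missing is a between-arm test of it.

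A reader might also infer that 0.928 was taken from the trial's own data. The same instruments were used in the Phase 1 survey, so the median could come from there. The reference to MMRM residuals supports a choice of method made after seeing repeated data. It does not establish where the cut came from.

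The label is an editorial matter, since renaming the category changes no estimate. Bootstrap intervals are one valid remedy among several for a bounded, skewed index.

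**Conclusion.** The concern holds in a limited form. For one of three primary outcomes, the only between-arm test named is on an odds scale at a threshold, while the hypothesis is about mean change. Non-normal residuals do not require that step. The wording suggests, without proving, that the step followed inspection of outcome data.

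It is tempting to say the split costs about a third of the information. The documents do not support that as a fact about this trial. It is the normal-theory value (36%), and the split is made precisely because normality was judged to fail. The supportable statement is a loss that depends on shape, roughly 0 to 39% over the assumed skewed and ceiling distributions, with no single figure following from the protocol. The mismatch with the hypothesis and the unexplained cut do not depend on that number. The change should be made: it is cheap and needs no new data.

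**What to change.** Make the primary EQ-5D analysis the continuous index in the same T0/T1 mixed model as the other outcomes. Report the arm-by-time mean difference in utility with a participant-level bootstrap confidence interval, or with robust standard errors and a small-sample correction.

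Keep any threshold analysis as secondary or descriptive. State which sample and time point gave the cut and whether it was chosen before outcome data were modelled. Do not label values from 0.928 to below 1 as free of problems.

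The cost is protocol wording and a bootstrap or robust option in the statistical software. The downside is that a mean is estimated on a skewed, bounded scale. Sandwich errors left uncorrected can also be too small at about 40 to 50 per arm, hence the bootstrap or the correction.

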#### 3.7.8 Appraisal Tools and Reporting

The mixed methods and the intervention studies will be appraised using evidence-based tools, Mixed Methods Appraisal Tool (MMAT) Version 2018 (Hong et al., 2018) and the Transparent Reporting of Evaluations with Non-randomised Designs (TREND), checklist, respectively (Des Jarlais et al., 2004). Critical appraisals are essential as an integral of good practice to ensure no potential threats to the validity of the research findings.

#### 3.7.9 Ethical consideration

Ethical approval was obtained from the University of Malaya Research Ethics Committee (UMREC). The protocol for this study was registered with the International Standard Randomised Controlled Trial Number (ISRCTN), an approved database by WHO, and was given a unique registration number (ISRCTN25880061). The benefits will be received by the respondents are health Promotion will be given to the participants. Referral for counselling and treatment. Whereas some respondents may may experience some emotional discomfort when answering certain questions in the mental health assessment questionnaires. Respondents can choose to stop answering the questions and contact the researchers as stated at the end of this information sheet.Other ethical issue concerned was the confidentiality of respondents with high scores for depression and anxiety symptoms rated by the screening tool. Given the high perceived self-stigma for mental health issues, two researchers will solely handle the referral letter for respondents. Participants will be called and reassured of the need for referral to the nearest health clinic or hospital. The referral letter will be emailed to the respondents.

